### **8.8.2. Post-Treatment Disease Follow-Up**

Participants who discontinue study treatment for a reason other than disease progression will move into the disease status follow-up period and should be assessed every 9 weeks  $\pm$  7 days by radiologic imaging to monitor disease status. Every effort should be made to collect information regarding disease status until:

- The start of new anticancer therapy: the start of the new treatment should be captured, but the participant should continue to have disease assessments until progressive disease (see below).
- Disease progression (confirmed by an ICR).
- Death.
- The end of the study.

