7.2.1.1. Response Criteria

Overall disease status will be categorized using RECIST v1.1 ([Eisenhauer et al 2009](#)) and RANO. Participants will have their overall response evaluated as CR, PR, SD, PD, or NE at each postbaseline radiological assessment. Assessments using RECIST v1.1 are based on changes in target lesions, nontarget lesions, and appearance of new lesions. Assessments using RANO are based on enhancing measurable lesions, enhancing nonmeasurable/nontarget lesions, nonenhancing T2/FLAIR/nontarget lesions, new lesions, steroid use, and clinical status.

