7.3. Analysis of the Secondary Efficacy Parameters

7.3.1. Progression-Free Survival

Progression-free survival is defined as the time from date of first dose of study drug to the earliest date of PD or death, whichever is first. Progressive disease is evaluated based on RECIST v1.1 or RANO, by the ICR. Partial death dates will be handled using the rules described in Section [4.1.4](#). Participants who are alive without progression before analysis cutoff date will be censored. Censoring for PFS will follow the algorithm outlined in [Table 2](#), which is

based on the FDA Guidance for Industry: Clinical Trial Endpoints for the Approval of Cancer Drugs and Biologics ([FDA 2015](#), [FDA 2018](#)).

Table 2: Evaluation and Censoring of Progression-Free Survival

Situation	Outcome	Date of Progression or Censoring
No baseline tumor assessments	Censored	Day 1
No valid postbaseline response assessments	Censored	Day 1
Progression documented between scheduled response assessments	Progressed	Date of first overall response of PD
No progression	Censored	Date of last valid radiologic assessment (not NE and not missing)
Study discontinuation for undocumented progression	Censored	Date of last valid radiologic assessment (not NE and not missing)
Study discontinuation for toxicity or other reason	Censored	Date of last valid radiologic assessment (not NE and not missing)

Table 2: Evaluation and Censoring of Progression-Free Survival (Continued)

Situation	Outcome	Date of Progression or Censoring
New anticancer treatment started	Censored	Date of last valid radiologic assessment (not NE and not missing) on/before starting a new anticancer treatment
Death before first progressive response assessment	Progressed	Date of death
Death between adequate response assessments	Progressed	Date of death
Death or progression after 2 or more missed assessments	Censored	Date of last valid radiologic assessment (not NE and not missing)

NE = not evaluable.

Progression-free survival data will be analyzed by the Kaplan-Meier method in Cohorts A and Cohort B, respectively. The number of participants who progressed or died and the number of participants censored will be summarized. The KM estimate of median PFS will be presented with its 95% CI. The 95% CI will be calculated using the generalization of Brookmeyer and Crowley's method ([1982](#)) with log-log transformation ([Klein and Moeschberger 1997](#)).

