7.3.2. Duration of Response

For objective responders, the duration of response is defined as the time from the date that a participant first achieves CR or PR based on RECIST v1.1 or RANO as assessed by ICR, until the date of first documented disease progression based on RECIST v1.1 or RANO as assessed by ICR, or death. Partial death dates will be handled using the rules described in Section [4.1.4](#).

Participants who are alive without progression before analysis cutoff date will be censored.

Censoring of DOR will follow the same algorithm as the censoring of PFS (see Section [7.3.1](#)).

Duration of response data will be analyzed by the Kaplan-Meier method in Cohorts A and B, respectively. The total number of responders, the number of participants who progressed or died, and the number of participants censored will be summarized. The KM estimate of median DOR will be presented with its 95% CI. The 95% CI will be calculated using the generalization of Brookmeyer and Crowley's method (1982) with log-log transformation (Klein and Moeschberger 1997).

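### As worded, SAP Table 2 censors a progression found after 2 or more missed scans on the date of the progression scan itself, which pushes Kaplan-Meier PFS and DOR upward

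*SAP*

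**What the plan says.** SAP 7.3.1 defines PFS from first dose to PD by central review or death, and sends all censoring to Table 2. The last row of that table covers "Death or progression after 2 or more missed assessments". Its outcome is censored. Its date column reads "Date of last valid radiologic assessment (not NE and not missing", with the bracket closed and nothing added.

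Other places that bear on how the row is read:

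- **SAP 7.2.1.1, response categories.** "Participants will have their overall response evaluated as CR, PR, SD, PD, or NE at each postbaseline radiological assessment". PD and NE are separate outcomes of a scan.
- **SAP Table 2, new-treatment row.** The date is "Date of last valid radiologic assessment (not NE and not missing) on/before starting a new anticancer treatment". This row has a time limit; the missed-assessment row has none.
- **SAP Table 2, second row.** "No valid postbaseline response assessments" leads to censoring at Day 1.
- **SAP 7.3.2.** "Censoring of DOR will follow the same algorithm as the censoring of PFS".
- **Protocol 10.4.2.** It refers PFS censoring to FDA guidance and gives no date rule of its own.
- **Protocol 8.8.2.** After new therapy starts, "the participant should continue to have disease assessments until progressive disease".

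Table 2 states no order of precedence between its rows.

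**The concern.** The usual reason to censor an event after a long gap is that nobody knows when, within the gap, it happened. Follow-up is then cut at the last point where the participant was known to be progression-free. The Table 2 row does the first half (it removes the event) but does not secure the second half. Its only test for a usable scan is that it is not NE and not missing. A scan read as PD passes that test, and it is the latest such scan.

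A programmer who follows the words therefore censors on the day progression was seen. The participant stays in the risk set through the whole gap, contributes no event, and lowers the estimated hazard at every scan date in between. The error runs one way, towards longer PFS and DOR. A programmer who follows the evident purpose would cut at the scan before the gap. The two would report different curves from the same data.

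This matters somewhat more for DOR, where numbers are small. At the planned rates Cohort A expects 60 x 0.35 = 21 responders and Cohort B 90 x 0.30 = 27, so one affected responder is 4.8% or 3.7% of the DOR sample.

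**Working it through.** The documents give no planned median, event count or missed-scan rate for PFS or DOR, so there is no figure of the plan's to reproduce. The check has two parts: worked records, and an assumption-based range.

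**Inputs from the documents.** Scans every 9 weeks, that is 63 days (Protocol 8.2.1). Study day = date minus Day 1 date + 1 (SAP 4.1.2), so a scan at week *w* falls on day 7*w* + 1. The baseline scan is taken at screening, Day -35 to Day -1 (Protocol Table 3).

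**Record 1, PFS.** SD at week 9 (day 64), weeks 18 and 27 missed, PD at week 36 (day 253).
- As worded: PD is not NE and not missing, so censored at day 253.
- Last valid scan before the gap: censored at day 64.
- Difference: 253 - 64 = 189 days, or 27 weeks, credited as progression-free without a scan.

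**Record 2, DOR.** PR at week 9 (day 64), confirmed at week 13 (day 92), weeks 18 and 27 missed, PD at week 36 (day 253). Counting both end days:
- As worded: 253 - 64 + 1 = 190 days.
- Before the gap: 92 - 64 + 1 = 29 days.

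**Record 3, death.** Same gap, but death instead of a PD scan. A death is not a scan, so the last valid scan is already the one before the gap. The row works.

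**Size for PFS (assumptions, not plan figures).** Exponential PFS with median *m* months (30.44 days each), scans every 63 days, no other censoring, and a share *q* of participants whose PD is found only after two missed scans. Let *r* = 2^(-63/(30.44*m*)) be the chance of passing one scan interval without progression. The curve is read at the third scan, day 189.
- As worded: PD in an affected participant is found at the third scan at the earliest, so all of them are still at risk there. The estimate is (1 - *q*)*r*^3 + *q*.
- Pre-gap: at scan *k* the events are (1 - *q*)(1 - *r*)*r*^(*k*-1) and the number at risk is (1 - *q*)*r*^(*k*-1) + *q* *r*^*k*. Each factor is *r*/(1 - *q* + *qr*), and the estimate is its cube.
- Example, *m* = 5 and *q* = 5%: *r* = 0.7506 and *r*^3 = 0.4228. As worded: 0.95 x 0.4228 + 0.05 = 45.2%. Pre-gap: (0.7506/0.9875)^3 = 43.9%.

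| Assumed median | q = 2% | q = 5% | q = 10% | q = 15% |
|---|---|---|---|---|
| 3 months | 25.3 vs 24.4 | 27.6 vs 25.2 | 31.4 vs 26.8 | 35.2 vs 28.4 |
| 5 months | 43.4 vs 42.9 | 45.2 vs 43.9 | 48.1 vs 45.6 | 50.9 vs 47.4 |
| 7 months | 55.0 vs 54.7 | 56.4 vs 55.6 | 58.7 vs 57.2 | 61.0 vs 58.9 |

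Entries are PFS at day 189 in percent, as worded vs pre-gap. The gap between the rules is 0.3 to 1.0 points at 2%, 0.8 to 2.4 at 5%, 1.5 to 4.7 at 10% and 2.1 to 6.8 at 15%. Both rules lie above the curve without gaps (*r*^3 = 42.3% at 5 months), because in this set-up gaps occur only with progressions.

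**Median.** On this grid the median is the same under both rules up to *q* = 10%. At 15% it moves by one scan interval, from day 189 to 252 (5 months) and from day 252 to 315 (7 months). Simulations of trials with 90 participants (300 per setting) show smaller, smoother shifts. With 6% to 7% affected and true medians of 3, 5 and 7 months, the typical estimate is 4.24 vs 4.17, 6.31 vs 6.24 and 8.41 vs 8.31 months. With 7% to 8% affected and true medians of 4 and 6 months, the averages are 5.8 vs 5.3 and 7.9 vs 7.4. Those last two are the sensitive cases, because weeks 18 and 27 fall at 126/30.44 = 4.14 and 189/30.44 = 6.21 months, so the estimate tips easily to the next scan. With under 1% affected the effect is negligible.

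**Edge case in the new-treatment row.** New therapy starts before the first postbaseline scan and scans then continue, as Protocol 8.8.2 asks. Valid postbaseline scans exist, so the Day 1 row does not literally apply. The last valid scan "on/before starting a new anticancer treatment" is the baseline scan, between Day -35 and Day -1, which gives a PFS time before the origin.

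**The case against.** The strongest reply is that the row is merely terse. It covers death and progression with one date expression, and censoring because of a gap makes sense only if the date lies before the gap. Table 2 is said to rest on FDA guidance, which is not available here, and an experienced programmer would probably do the sensible thing. The intent is indeed evident. But the plan states a date rule, the rule gives a biased result when followed literally, and nothing elsewhere in either document supplies the missing limit. The new-treatment row shows that the authors added a limit where they thought of one.

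The reply is right on size. The gap shares above are assumed. Protocol Appendix E foresees missed assessments during the pandemic but gives no imaging rate, and Protocol 8.2.1 keeps imaging at 9-week intervals despite cycle delays. Two missed scans in a row mean about 27 weeks without imaging, against an estimated participation of about 6 months. Landmark PFS rates are not a planned summary. They serve here only to show how far the plotted curve moves.

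A reader might infer more than the documents support:

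- **That the missed-assessment row yields times before Day 1.** If the PD scan is set aside and no earlier postbaseline scan exists, the row for "No valid postbaseline response assessments" is the natural reading and gives Day 1. One cannot exclude the PD scan to reach baseline and still count it as a valid postbaseline scan.
- **That DOR needs its own lower bound.** Every responder has a response scan after baseline, so the baseline scan can never be the DOR censoring date.
- **That the row must say the missed scans are consecutive.** The existing phrase ordinarily means that.

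**Conclusion.** The point holds for the progression half of the row, and for DOR by inheritance: if programmed as written, the event is deleted and the unobserved gap counts as progression-free time. The death half is sound.

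The size depends on how many participants have such gaps, which the documents do not give. At an assumed 5% to 10% and medians of 3 to 7 months, the curve at day 189 is 0.8 to 4.7 points too high. The median shift is typically about 0.1 months, reaching about 0.5 when the true median lies next to a scan date. At 15% the shift is larger, and with rare gaps there is almost none.

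It would be too strong to say that PFS and DOR will be wrong. They will be wrong only if the row is coded literally and such records occur. It would also be wrong to read this as a threat to the trial's main conclusion. PFS and DOR are secondary and carry no hypothesis test, and the ORR test does not use Table 2. The new-treatment case is a minor edge case: Protocol 8.2.1 lists the start of new therapy as an end point for imaging, so it arises only where scans continue under 8.8.2.

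**What to change.** Change two date entries in SAP Table 2 before database lock:

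1. **Missed-assessment row:** censor at the last valid scan before the missed assessments, or at Day 1 if no valid postbaseline scan precedes them.
2. **New-treatment row:** keep the present limit and add Day 1 as the date when there is no valid postbaseline scan on or before the new treatment.

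DOR then follows through SAP 7.3.2 without separate wording. The cost is two lines of text and the matching derivation code, with no new data. Reported medians may come out slightly shorter.

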7.3.2. Duration of Response

For objective responders, the duration of response is defined as the time from the date that a participant first achieves CR or PR based on RECIST v1.1 or RANO as assessed by ICR, until the date of first documented disease progression based on RECIST v1.1 or RANO as assessed by ICR, or death. Partial death dates will be handled using the rules described in Section [4.1.4](#).

Participants who are alive without progression before analysis cutoff date will be censored.

Censoring of DOR will follow the same algorithm as the censoring of PFS (see Section [7.3.1](#)).

Duration of response data will be analyzed by the Kaplan-Meier method in Cohorts A and B, respectively. The total number of responders, the number of participants who progressed or died, and the number of participants censored will be summarized. The KM estimate of median DOR will be presented with its 95% CI. The 95% CI will be calculated using the generalization of Brookmeyer and Crowley's method (1982) with log-log transformation (Klein and Moeschberger 1997).

7.3.3. Overall Survival

Overall survival is defined as the time from date of first dose of study drug to the date of death due to any cause. Date of death will be determined using the Death Report, the Survival Follow-Up, and the Participant Status eCRFs. Participants who are lost to follow-up or still alive at the time of analysis will be right-censored at the earlier of the date the participant was last known alive and the clinical data cutoff date for the analysis. The last known alive date is defined as the later of the last study visit and the date the participant was last known alive from the Survival Follow-Up and Participant Status eCRFs. Partial death dates will be handled using the rules described in Section 4.1.4.

Overall survival will be analyzed by the Kaplan-Meier method in Cohorts A and B, respectively. The number of participants who died and the number of participants censored will be summarized. Median survival will be estimated using the Kaplan-Meier method. The 95% CIs for median survival time will be calculated using the generalization of Brookmeyer and Crowley's method (1982) with log-log transformation (Klein and Moeschberger 1997).

7.4. Other Efficacy Analyses

7.4.1. Largest Percentage Reduction in Sum of Diameters of Target Lesions

For each participant in the efficacy evaluable population with target lesions at baseline, target lesion sizes will be measured by sum of diameters. The best percentage change from baseline, defined as the largest decrease in target lesion size for each participant, will be summarized descriptively, and a waterfall plot of the best percentage change will be generated.

Per RECIST criteria, target lesions considered "too small to measure" will be assigned a default value of 5 mm for purposes of this analysis. Likewise, target lesions identified as "not present" at postbaseline assessments will be assigned 0 mm for this analysis. In the event a target lesion is unaccounted for in a particular postbaseline timepoint (ie, assessment missing or not evaluable), then the overall sum of diameters for target lesions will not be evaluable for that postbaseline timepoint.

8. SAFETY AND TOLERABILITY

[Appendix A](#) provides a list of data displays. Sample data displays are included in a separate document.

8.1. General Considerations

The analyses for this section will be provided for the safety population. Summary tables may be replaced with listings when appropriate. For instance, an AE frequency table may be replaced with a listing if it only contains a few unique PTs reported on relatively few participants.

8.2. Adverse Events

8.2.1. Adverse Event Definitions

A TEAE is any AE either reported for the first time or worsening of a pre-existing event after first dose of study drug until 30 days after the last dose of study drug. Analysis of AEs (as discussed below) will be limited to TEAEs, but data listings will include all AEs regardless of their timing in relation to study drug administration. For purposes of analysis, all AEs will be considered TEAEs unless the AE can unequivocally be defined as not treatment emergent.

Adverse events will be tabulated by MedDRA PT and SOC. Severity of AEs will be graded using the NCI CTCAE v5.0. The CTCAE reporting guidelines and grading details are available on the CTEP website.

A grading (severity) scale is provided for each AE term. If the toxicity is not included in the CTCAE v5.0 criteria, it will be graded on a scale of 1 to 5 as follows: 1 = mild, 2 = moderate, 3 = severe, 4 = life-threatening, and 5 = fatal. All toxicities will be graded based on the worst level reached, not the level they may have reached if they had not been treated. When the intensity of an AE changes over time for a reporting period (eg, between visits), each change in intensity will be reported as an AE until the event resolves.

The subset of AEs considered by the investigator to be related to study drug will be considered to be treatment-related AEs. If the investigator does not specify the relationship of the AE to study drug, the AE will be considered to be treatment-related. The incidence of AEs and treatment-related AEs will be tabulated. In addition, SAEs will also be tabulated.

Any missing onset date, causality, or severity must be queried for resolution. Unresolved missing causality and severity will be handled according to the following rules:

- An unresolved missing causality will be considered treatment-related.
- An unresolved missing severity will be identified as an unknown severity.

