### 8.3.1. Adverse Events

Adverse events will be monitored from the time the participant signs the ICF until at least 30 to 35 days after the last dose of study drug or until the start of new anticancer therapy, whichever occurs first. Adverse events that begin or worsen after informed consent should be recorded on the Adverse Events Form in the eCRF regardless of the assumption of a causal relationship with the study drug. Conditions that were already present at the time of informed consent should be recorded on the Medical History Form in the eCRF. Adverse events (including laboratory abnormalities that constitute AEs) should be described using a diagnosis whenever possible rather than by individual underlying signs and symptoms.

Adverse events will be reported by the participant (or, when appropriate, by a caregiver, surrogate, or the participant's legally authorized representative). The investigator and any qualified designees are responsible for detecting, documenting, and recording events that meet the definition of an AE or SAE and remain responsible for following-up on AEs that are serious, considered related to the study treatment/procedures, or that caused the participant to discontinue study drug. Care will be taken not to introduce bias when detecting AEs and/or SAEs.

Open-ended and nonleading verbal questioning of the participant, such as "How are you feeling?" is the preferred method to inquire about AE occurrences. Adverse events may also be detected when they are volunteered by the participant during the screening process or between visits, or through physical examinations, laboratory tests, or other assessments. The definition, reporting, and recording requirements for AEs are described in Section [9](#).

All SAEs will be recorded and reported to the sponsor or designee within 24 hours. The investigator will submit any updated SAE data to the sponsor within 24 hours of it being available.

After the initial AE/SAE report, the investigator is required to proactively follow each participant at subsequent visits/contacts. All SAEs will be followed until resolution, stabilization, the event is otherwise explained, or the participant is lost to follow-up (as defined in Section 7.3).

For Japanese participants only, the relationship of the adverse event to phosphate binder(s) should also be collected on the Adverse Events Form in the eCRF.

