## **8.8. Follow-Up**

### **8.8.1. Safety Follow-Up**

The safety follow-up period is the interval between the EOT visit and the scheduled follow-up visit, which should occur 30 to 35 days after the EOT visit (or after the last dose of study treatment if the EOT visit was not performed). Adverse events and SAEs must be reported up until 1) at least 30 days after the last dose of study treatment, the date of the follow-up visit, or the start of a new anticancer therapy or 2) until toxicities resolve, return to baseline, or are deemed irreversible, whichever is longer. Reasonable efforts should be made to have the participant return for the follow-up visit and report any AEs that may occur during this period. If the participant cannot return to the site for the safety follow-up visit (eg, lives far away), the participant should be contacted by telephone for assessment of AEs and SAEs. Sites should document this contact in the source.

If a participant is scheduled to begin a new anticancer therapy before the end of the 30- to 35-day safety follow-up period, the safety follow-up visit should be performed before the new anticancer therapy is started. Once new anticancer therapy has been initiated, the participant will move into the survival follow-up period.

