### 9.4. Reporting of Serious Adverse Events

Regardless of suspected causality (eg, relationship to study drug or study procedure[s]), all SAEs occurring after the participant has signed the ICF through 35 days after the last dose of study treatment **or** until the participant starts a new anticancer therapy, whichever occurs earlier) must be reported to the sponsor (or designee) within **24 hours** of learning of its occurrence, unless otherwise specified by the Protocol. The investigator will submit any updated SAE data to the sponsor (or designee) within 24 hours of it being available. For Japan, this information must also be reported immediately to the head of the study site.

Investigators are not obligated to actively seek AE or SAE information after conclusion of the study participation. However, if the investigator learns of any SAE, including a death, at any time after a participant has been discharged from the study, and he/she considers the event to be reasonably related to the study treatment or study participation, the investigator must notify the sponsor (or designee) within 24 hours of becoming aware of the event.

After the initial AE/SAE report, the investigator is required to proactively follow each participant at subsequent visits/contacts. All SAEs will be followed until resolution, stabilization, the event is otherwise explained, or the participant is lost to follow-up (as defined in Section [7.3](#)).

Prompt notification by the investigator to the sponsor of a SAE is essential so that legal obligations and ethical responsibilities towards the safety of participants and the safety of a study treatment under clinical investigation are met.

If the SAE is not documented in the [IB](#) or the study drug (new occurrence) and is thought to be related to the sponsor's study drug, the sponsor or its designee may urgently require further information from the investigator for reporting to health authorities. The sponsor or its designee may need to issue an Investigator Notification to inform all investigators involved in any study with the same drug that this SAE has been reported. Suspected Unexpected Serious Adverse Reactions will be collected and reported to the competent authorities and relevant ethics committees in accordance with Directive 2001/20/EC, or as per national regulatory requirements

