#### **10.4.3. Safety Analyses**

[figure not shown]
Safety analyses will be conducted for the safety population. Adverse events will be coded by the MedDRA dictionary, and TEAEs (ie, AEs reported for the first time or worsening of a pre-existing event after first dose of study drug/treatment) will be tabulated by preferred term and system organ class for all events, related events, and events of Grade 3 or higher.

Quantitative safety variables and their changes from baseline (laboratory, vital signs, etc) will be summarized with descriptive statistics. Clinically notable abnormal values will be flagged and tabulated based on predefined criteria.

The clinical laboratory data will be analyzed using summary statistics; no formal treatment group comparisons are planned. In addition, distributions of key laboratory parameters may be plotted over time; these values will also be classified into CTCAE toxicity grades and tabulated. Descriptive statistics and mean change from baseline will be determined for vital signs at each assessment time. Vital sign results will be reviewed for clinically notable abnormalities.

Descriptive statistics and mean change from baseline will be determined for each ECG parameter at each assessment time. Electrocardiogram results will be reviewed for clinically notable abnormalities according to predefined criteria (see Section 8.3.4). Participants exhibiting clinically notable ECG abnormalities will be listed.

Measures of exposure of study drug will be summarized by means of summary statistics.

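### The SAP ends the TEAE window 30 days after last dose although SAEs must be reported to Day 35, so dated Day 31 to 35 events reach the listings but no AE table, and the difference is not declared

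*SAP*

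**What the plan says.** **SAP 8.2.1** sets the TEAE period as "after first dose of study drug until 30 days after the last dose of study drug". It then states that "Analysis of AEs (as discussed below) will be limited to TEAEs", while "data listings will include all AEs regardless of their timing in relation to study drug administration". Uncertain cases go in: "all AEs will be considered TEAEs unless the AE can unequivocally be defined as not treatment emergent".

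**SAP 8.2.3 and Appendix A (Tables 3.2.1 to 3.2.23)** build all AE tables on TEAEs, including the serious tables (3.2.8, 3.2.9) and the fatal table (3.2.14). SAP 8.2.1 says that SAEs will be tabulated, but the tables actually planned cover serious TEAEs only. One line of 8.2.3 names treatment-related AEs without the treatment-emergent qualifier; the matching Table 3.2.10 restores it.

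**Protocol 10.4.3** defines TEAEs as "AEs reported for the first time or worsening of a pre-existing event after first dose of study drug/treatment", with no end date. The protocol's abbreviation list does the same.

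**Protocol 8.3.1** monitors AEs "until at least 30 to 35 days after the last dose of study drug", and **Protocol 9.4** requires SAE reporting "through 35 days after the last dose of study treatment". Both stop sooner if new anticancer therapy begins.

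**Protocol 8.8.1** places the safety follow-up visit at a time "which should occur 30 to 35 days after the EOT visit", or counts from the last dose if there was no EOT visit.

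**SAP 10.1** records changes to protocol-defined analyses as not applicable.

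**The concern.** TEAE occurrence is a named secondary endpoint in both documents, and the two define it differently. The SAP's version is the narrower one. Compared with the protocol's open-ended definition, it can only leave TEAE, serious TEAE and fatal TEAE counts unchanged or lower them. The events at issue include SAEs that sites are obliged to report. A reader of the study report who takes the tables to show all SAEs reported under the protocol would be mistaken, and nothing in the SAP would alert them.

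A version lag is unlikely to explain it. The SAP was written on Amendment 2 but states that it applies to later amendments. The visible items in the Amendment 3 summary of changes include none to the TEAE definition in 10.4.3.

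**Working it through.** The plan gives no computed figure to reproduce. The check compares time windows, counting days from the last dose.

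**Inputs**
- End of TEAE window: Day 30 (SAP 8.2.1).
- End of mandatory SAE reporting: Day 35, or new anticancer therapy if earlier (Protocol 9.4).
- Safety visit: EOT visit + 30 to 35 days (Protocol 8.8.1 and Table 3).
- Estimated individual participation: about 6 months (Protocol Table 2).

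**Step 1. Size of the gap.** 35 − 30 = 5 days, namely Days 31 to 35. As a share of the post-dose SAE period, 5/35 = 14.3%. As a share of estimated participation, using the SAP's 30.44 days per month, 6 × 30.44 = 182.6 days and 5/182.6 = 2.7%. Both are shares of calendar time, not of events.

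**Step 2. How the rule treats particular events.** The days below are illustrative.

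| Event | In the TEAE tables? |
|---|---|
| Onset Day 25, first reported at a Day 33 visit | Yes; onset decides, not the visit date |
| Onset date missing or ambiguous | Yes, by the default rule |
| Fully dated onset on Day 33, serious or not | No; the date is unequivocally outside |
| Onset Day 25, worsening on Day 33 | The Day 25 record counts; the Day 33 record does not if flagged by its own date |

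The last row arises because Protocol 9.3 and SAP 8.2.1 record each change in severity as a separate AE. The maximum-severity and Grade 3 or higher tables could then miss the worse grade of an event that is otherwise counted.

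**Step 3. Where the excluded events go.** Listings 2.7.1 to 2.7.7 include AEs whatever their timing. None of Tables 3.2.1 to 3.2.23 does.

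**Step 4. Where the safety visit falls.** Visit day = EOT lag + 30 to 35. The lag is not given, so these values are assumptions:
- lag 0: Days 30 to 35
- lag 7: Days 37 to 42
- lag 14: Days 44 to 49

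A visit can also come before Day 30, because Protocol 8.8.1 asks for it to be done before new anticancer therapy that is scheduled within the follow-up period. The visit date is thus a variable end-point. A window ending at Day 35 matches the SAE reporting rule, but it would not reach a visit counted from a late EOT visit.

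**The case against.** The best defence is that 30 days is deliberate. Protocol 8.8.1 gives at least 30 days after last dose as a minimum for AE reporting, the SAP exists to add detail to analyses that the protocol outlines, and a fixed cut-off gives every participant the same window. That is a fair reason for choosing 30 days. It does not explain why SAEs collected by rule to Day 35 have no table, or why SAP 10.1 is silent.

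The defence is right to limit the consequences. A reader might infer four stronger things that the documents do not support:

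- *That most of what the safety visit finds is discarded.* Onset or worsening decides, so events that began by Day 30 stay in. The visit's ECG and vital-sign values are summarised by scheduled visit with no 30-day cut (SAP 4.1.6, 8.4, 8.5), and laboratory shift tables run to the worst postbaseline grade (SAP 8.3.2).
- *That only a visit held exactly on Day 30 is inside the window.* Visits brought forward before new anticancer therapy can be earlier, and the visit date is not the criterion in any case.
- *That late deaths vanish.* They count in overall survival for Cohorts A and B (SAP 7.3.3) and are due to appear in the deaths listing (2.6.1). What is missing is their place in the fatal TEAE table.
- *That the 9.6% fatal TEAE rate in Protocol 2.3 (64 of 665) shows Day 31 to 35 deaths to be common.* That figure carries no timing. Its commonest terms were general physical health deterioration (15) and disease progression (10), with malignant neoplasm progression in 4 more. Protocol 9.1 keeps events related to progression of the study cancer out of AE reporting in this trial.

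The 14% is likewise calendar time, and collection stops at new anticancer therapy, which shrinks the gap further.

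**Conclusion.** The point holds. Followed as written, the SAP leaves AEs, SAEs and fatal AEs with a known onset or worsening date on Days 31 to 35 out of every AE table, although SAEs in that period must be reported. It does so without declaring a departure from the protocol's open-ended TEAE definition. The direction is known: counts can only be equal or lower. The size is not: 5 of 35 days is the length of the gap, and no event count follows from it. The effect is probably small. The excluded events remain in the listings, so the fault lies in tabulation and declaration and no data are lost. The conclusion assumes that the TEAE flag is programmed from onset or worsening dates exactly as SAP 8.2.1 reads. The change is worth making because the conflict is plain, it touches a named secondary endpoint, and it is cheap to remove.

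**What to change.** Preferred: in SAP 8.2.1, end the TEAE window 35 days after last dose or at the start of new anticancer therapy, whichever is earlier, to match Protocol 9.4. State that a worsening recorded as its own AE is judged by its own date within that window. Because the protocol's definition has no end date, note the end date in SAP 10.1.

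Alternative: keep 30 days, declare it in SAP 10.1 with a reason, and add tables of serious and fatal AEs through Day 35.

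Do not tie the window to the safety visit. Its length would then depend on EOT lag and attendance.

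Cost: SAP wording and a date rule in the TEAE flag, or two added tables. AE counts would probably rise slightly. Collection of non-serious AEs on Days 31 to 35 varies with the visit date, so those counts would be less uniform than the SAE counts. Ending at new anticancer therapy would also drop any event recorded after that start but by Day 30, which the SAP now counts. Few are expected, since routine collection stops there under Protocol 8.3.1 and 9.4.
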